8.2 Responsibility for Analyses/In-house Blinding

The statistical analyses of the data obtained from this study will be the responsibility of the Clinical Biostatistics department of the Sponsor.

The trial is open label, ie, subjects, investigators, and Sponsor personnel will be aware of subject treatment assignment after each subject is enrolled and treatment is assigned. Allocation to treatment will not be randomized.

8.3 Hypotheses/Estimation

Objectives and hypotheses of the study are outlined in Section 3.0.

8.4 Analysis Endpoints

Efficacy and safety endpoints are listed below, followed by descriptions of selected endpoints.

8.4.1 Efficacy/Pharmacokinetic Endpoints

ORR in subjects treated with MK-1454 in combination with pembrolizumab as assessed by investigator using RECIST 1.1 criteria is a secondary endpoint for Part II of the trial. PFS and OS are exploratory endpoints in this study. Details of the statistical analysis plan for exploratory endpoints will be documented in the sSAP. A description of efficacy measures is provided in Section 4.2.3.

ORR is defined as the proportion of subjects who have achieved confirmed CR or PR.

Progression-free survival is defined as the time from the first dose of study treatment to the first documented disease progression or death due to any cause, whichever occurs first.

OS is defined as the time from the first dose of study treatment to death due to any cause. Subjects who do not die will be censored on the date of the last study assessment or contact.

ORR for noninjected lesions is defined as the proportion of participants who have achieved at least 30% reduction in the sum of diameters of noninjected lesions, among participants with target noninjected lesions identified at baseline.

PK endpoints include concentrations of MK-1454 and pembrolizumab, as well as any derived PK parameters.

8.4.2 Safety Endpoints

The primary safety endpoint is the number/proportion of subjects with DLT(s), AE(s), and who discontinue study treatment due to AE(s). A description of safety measures is provided in Section 4.2.3.2.

8.5 Analysis Populations

087V73

8.5.1 Safety Analysis Population

The ASaT population will be used for the analysis of safety data in this study. The ASaT population consists of all subjects who received at least one dose of study treatment. In case

Protocol/Amendment No.: 001-08

of treatment administration errors, subjects will be analyzed according to the treatment they actually received. The DLTe population includes ASaT subjects that were observed for safety for 21 days after the first dose of assigned treatment or experienced a DLT prior to 21 days after the first dose of assigned treatment. The replacement subjects will also be considered evaluable if the above specified criteria are met.

At least one laboratory or vital sign measurement obtained subsequent to at least 1 dose of study treatment is required for inclusion in the analysis of each specific parameter. To assess change from baseline, a baseline measurement is also required.

8.5.2 Pharmacokinetic Analysis and Target Engagement Populations

The PP population will be used for analysis of PK and target engagement data in this study. The PP population consists of the subset of subjects who complied with the protocol sufficiently to ensure that the data they generated will be likely to exhibit the effects of treatment, according to the underlying scientific model. Compliance covers such considerations as exposure to treatment, availability of measurements, and absence of major protocol violations. Major protocol violators will be identified, to the extent possible, by individuals responsible for data collection/compliance, and its analysis and interpretation. Any subjects or data values excluded from analysis will be identified, along with the reasons for exclusion, in the CSR. At the end of the study, all subjects who were compliant with the study procedures and have available data from at least one treatment will be potentially included in the PP analysis dataset.

8.5.3 Efficacy Analysis Populations

The FAS population will be used for analysis of the secondary and exploratory efficacy data in this study. It consists of all subjects with a baseline scan that demonstrated measurable disease by investigator assessment, and who were administered a dose of study medicine.

A supportive approach using modified FAS population may be performed for the efficacy endpoints. The modified FAS population includes FAS subjects without substantial dose interruption as defined in the sSAP.

8.6 Statistical Methods

087V73

8.6.1 Statistical Methods for Efficacy Analyses

For the secondary endpoint of ORR, the point estimate and 95% CI will be evaluated in Part II subjects treated with MK-1454 in combination with pembrolizumab at the RP2D for each tumor cohort separately, using an exact method based on the binomial distribution (Clopper-Pearson Interval). Other exploratory endpoints (eg, PFS) may also be examined within each expansion cohort. Of note, efficacy analyses for each Part II expansion cohort will pool Part I subjects who meet the inclusion criteria for the respective Part II tumor type and received the same dose level of MK-1454 in combination with pembrolizumab.

8.6.2 Statistical Methods for Safety Analyses

Safety and tolerability will be assessed by clinical review of all relevant parameters including AEs, SAEs, laboratory tests, vital signs, ECG measurements, and physical examinations.

MK-1454-001-08 Final Protocol 27-Jul-2021 Confidential

Protocol/Amendment No.: 001-08

AEs will be summarized by counts and frequencies for each dose level, arm, and cohort. Laboratory tests, vital signs, and other safety endpoints will be summarized as appropriate.

Dose-limiting toxicities will be listed, and further summarized by dose level and arm. The pool adjacent-violators-algorithm [31], which forces the DLT rate estimates to be nondecreasing with dose levels and pools adjacent violators for weighted estimates by sample size, will be used to estimate the DLT rates across doses in each treatment arm. The estimates of the DLT rates among subjects treated at the MTDs (or MADs) and the 80% Bayesian credible intervals based on a prior distribution of Beta (1,1) for the estimates will be provided.

8.6.3 Summaries of Baseline Characteristics, Demographics, and Other Analyses

8.6.3.1 Demographic and Baseline Characteristics

Demographic variables, baseline characteristics, primary and secondary diagnoses, and prior and concomitant therapies will be summarized.

8.6.3.2 Pharmacokinetics and Pharmacodynamics Modeling Analysis

Plasma concentrations of MK-1454 will be summarized by planned visit and time for each dose separately; PK parameters will be summarized by dose. For pembrolizumab, serum concentrations will be compared to the historical monotherapy pembrolizumab data. Details of statistical analysis of pharmacokinetics-pharmacodynamics analyses will be documented in the sSAP.

8.7 Interim Analyses

An administrative analysis may be conducted to enable future trial planning at the Sponsor's discretion and data will be examined on a continuous basis to allow for dose escalation and confirmation decisions.

An interim futility check will be performed for each of the selected solid tumor cohorts in Part II (Cohorts A through C). For Cohorts A, B, and C, if there are no responders among approximately the first 15 evaluable subjects, the cohort may be stopped early for futility. For Cohort C, an additional futility check may be performed if applicable for the first 30 evaluable subjects. If there is one or less responder among the first 30 evaluable subjects in Cohort C, the Cohort may be stopped early for futility. An evaluable subject has at least one postbaseline imaging assessment. If the true response rate is 10%, there is an 80% chance to observe at least 1 responder among 15 subjects, and an 82% chance to observe at least 2 responders among 30 subjects.

The futility bar is not binding, and the totality of the data will be evaluated before making a decision to discontinue enrollment. The data will be analyzed on a continuous basis and enrollment will not be paused when interim analyses are performed.

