Tumor Imaging, RECIST, irRECIST, and/or itRECIST Response Assessment Cohort B	X									X	X	To be performed at 9 weeks (± 7 days) after the first dose, and then every 9 weeks thereafter. Tumor imaging (CT, PET/CT, or MRI, as indicated for tumor type), and medical photography should be performed on the same schedule, following calendar days , and should not be adjusted for
Medical Photography (Cutaneous Lesions)	X									X	X	delays in cycle starts. Continue imaging schedule until disease progression, discontinuation, or EOT. Medical photography can be performed more often as medically warranted.
	Safety Asse	essme	nts an	d Proc	edure	3						See Procedures Manual for Collection And Management of Samples.
AE Monitoring		(=									- →	
Full Physical Examination	X	X			X			X			X	
Directed Physical Examination			X	X		X	X					
Weight	X	X			X			X			X	
Height	X											
12-lead ECG	X											

Protocol/Amendment No.: 001-08

Trial Period	Screening		Treatment Phase MK-1454 Cycle = CCC then Q3W; or Q3W Pembrolizumab Cycle = 21 Days Cycle 4									
Cycle			Cvcle	1	(Cvcle 2	2	and		and	Notes	
Scheduling Day	-28 to -1	1	8	15	1	8	15	1	8	15	1	
Scheduled Window		±3	±3	±3	±3	±3	±3	±3	±3	±3	±3	
Vital Signs (temperature, pulse, respiratory rate, blood pressure, and oxygen (O ₂) saturation)	X	X	X	X	X	X	X	X	X	Х	X	Collect VS predose within 1 h (± 30 min) of MK-1454 administration at each treatment visit. Collect VS postdose on C1D1 at 2, 4, 6, and 8h (± 30 min for each time point) after MK-1454 administration. At each subsequent treatment visit, collect VS at 1 h (±15 min) after MK-1454 administration. Additional VS monitoring may be obtained as clinically indicated.
ECOG Performance Status	X	X			X			X			X	Additional ECOG can be performed as clinically indicated.
Tumor Markers	X	X			X			X			X	Specific tumor markers (eg, CEA, CA-125, CA-19-9, or alpha fetoprotein) to be obtained as clinically indicated.
CBC with Differential	X	X	X	X	X	X	X	X	X	X	X	Perform all screening clinical laboratory tests within 7 days
PT/INR and PTT or aPTT	X	X			X			X			X	prior to C1D1. Tests performed prior to the subject signing consent as part of routine clinical management are acceptable
Chemistry Panel	X	X	X	X	X	X	X	X	X	X	X	in lieu of a screening test, if the test is performed within the
LDH, GGT	X	X			X			X			X	specified time frame. For C1D1 and subsequent cycles

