7.1.2.6 Tumor Imaging and Medical Photography

The initial PET/CT scan or MRI for solid tumor imaging as well as medical photography for cutaneous lesions must be performed within 28 days prior to enrollment, and the site study team must confirm that the subject has measurable disease as defined by RECIST version 1.1, IWG revised criteria, or ISCL criteria to confirm eligibility. In subjects with CTCL, it is recommended that CT and PET scans be performed at screening.

Part I – Dose Escalation and Confirmation

For Arms 1, 2, and 3 (Part I), tumor imaging and/or medical photography should be repeated every 9 weeks for solid tumors or every 12 weeks for lymphomas from the first dose of treatment. For subjects with CTCL, medical photography will be performed at each treatment cycle, however, tumor imaging will be repeated only to document and confirm PR, CR, or PD.

Part II – Expansion Cohorts

For Cohort A (HNSCC) and Cohort B (TNBC), imaging will begin at 9 weeks and occur every 9 weeks thereafter. Imaging for HNSCC should include the head, neck, chest, and abdomen at all timepoints. Imaging of the pelvis is optional.

Solid tumor imaging should be acquired by CT (with PET for CTCL, as clinically indicated). For subcutaneous lesions, imaging by either MRI or CT is to be obtained at screening and at the imaging time points outlined in Section 2 SoA for assessment of response. MRI should be used when CT is contraindicated or for imaging of the brain. The same imaging technique and the same imaging modality with/without the use of contrast should be performed for assessment of response in a subject throughout the trial to optimize visualization of existing and new tumor burden. Tumor imaging schedule is based on **calendar days** from the first drug administration, and will not be postponed due to delays in treatment cycles. Additional tumor imaging and/or medical photography may be performed as clinically indicated.

Please refer to the Site Imaging Manual for detailed instructions regarding tumor imaging and medical photography.

A central imaging vendor will be made available for possible future independent review.

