- Additional new nontarget progression since last evaluation

In subjects who have initial evidence of radiological PD, it is at the discretion of the investigator whether to continue a subject on study treatment until repeat imaging is obtained. This clinical judgment decision should be based on the subject's overall clinical condition, including performance status, clinical symptoms, and laboratory data. Subjects may receive study treatment while waiting for confirmation of PD, if they are clinically stable as defined by the following criteria:

- Absence of symptoms and signs indicating clinically significant progression of disease, including worsening of laboratory values
- No decline in ECOG performance status
- Absence of rapid progression of disease
- Absence of progressive tumor at critical anatomical sites (eg, cord compression) requiring urgent alternative medical intervention

When feasible, subjects should not be discontinued until progression is confirmed. This allowance to continue treatment despite initial radiologic progression takes into account the

Protocol/Amendment No.: 001-08

observation that some subjects can have a transient tumor flare in the first few months after the start of immunotherapy, and still have a subsequent disease response. Subjects who are deemed clinically unstable are not required to have repeat imaging for confirmation of PD.

NOTE: In subjects who discontinue study therapy without documented disease progression, every effort should be made to continue monitoring of their disease status by radiologic imaging every 9 weeks (\pm 7 days) until: (1) the start of new anticancer treatment, (2) disease progression (3) death, or (4) the end of the study, whichever occurs first.

Confirmation of PR and CR is required at least 4 weeks after the initial response assessment of PR and CR.

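### Do the 80% and 82% futility figures in Section 8.7 fail because one scan makes a subject evaluable while response needs later confirmation?

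*Combined protocol and SAP*

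**What the plan says.** Section 8.7 (Interim Analyses) plans a futility check in each Part II cohort at about 15 evaluable subjects; with no responders, the cohort may be stopped. On evaluability it says "An evaluable subject has at least one postbaseline imaging assessment". It adds: "For Cohort C, an additional futility check may be performed if applicable for the first 30 evaluable subjects"; there the bar is one responder or none. For a true rate of 10% it gives an 80% chance of at least 1 responder among 15, and "an 82% chance to observe at least 2 responders among 30 subjects". It then limits the force of both rules: "The futility bar is not binding, and the totality of the data will be evaluated before making a decision to discontinue enrollment". Data are reviewed continuously and accrual does not stop for the checks.

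The word responder is not defined in Section 8.7. The endpoint definition in Section 8.4.1 reads "ORR is defined as the proportion of subjects who have achieved confirmed CR or PR". Section 7.1.2.7.1 adds "Confirmation of PR and CR is required at least 4 weeks after the initial response assessment of PR and CR". The Part II schedule in Section 6.2.1 places imaging as follows: "To be performed at 9 weeks (± 7 days) after the first dose, and then every 9 weeks thereafter". Section 7.1.2.6 gives the same interval for Cohorts A and B.

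**The concern.** A subject becomes evaluable at the first scan, around week 9. If that scan shows a partial response, the next scheduled scan is around week 18, so confirmation comes then unless an extra scan is done at least 4 weeks after the first. If the check counts only confirmed responses, subjects with one scan sit in the denominator with no chance of being in the numerator. The real chance of clearing the bar is then below 80% or 82%.

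At stake is how a result of 0 in 15 is read. The stated figure makes it roughly a 1-in-5 event for a treatment with a 10% response rate. If several of the 15 could not yet count, it is more common than that and says less about inactivity, so an active cohort might be closed on immature data.

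The second worry is that Cohort C can meet two bars, and the chance of clearing both cannot be read from two separate probabilities.

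**Working it through.** **Inputs.** Section 8.7: true rate 0.10; bars of at least 1 in 15 and at least 2 in 30. Section 7.1.2.7.1: confirmation at least 4 weeks later. Section 6.2.1: scans every 9 weeks. The documents give neither an accrual rate nor the number of subjects with a single scan at the time of a check, so those counts are assumptions below.

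**1. The plan's own figures.**
- P(at least 1 of 15) = 1 − 0.9^15 = 1 − 0.2059 = 0.7941.
- P(at least 2 of 30) = 1 − 0.9^30 − 30 × 0.1 × 0.9^29 = 1 − 0.0424 − 0.1413 = 0.8163.

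Both reproduce; the first rounds strictly to 79%, which is immaterial.

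**2. Confirmed responses only, with m subjects having one scan and no chance to qualify (m assumed).** Replace 15 by 15 − m and 30 by 30 − m.

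| m | At least 1 of 15 | At least 2 of 30 |
|---|---|---|
| 0 | 79.4% | 81.6% |
| 1 | 77.1% | 80.1% |
| 3 | 71.8% | 76.7% |
| 5 | 65.1% | 72.9% |
| 8 | 52.2% | 66.1% |

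This treats each one-scan subject as losing a full 10% chance. That is too pessimistic where a subject has one scan because of progression, death or discontinuation: such subjects are mostly non-responders already reflected in the 10% rate. The lower rows therefore overstate the loss unless every one-scan subject is still on study and awaiting a second scan.

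**3. Unconfirmed responses counted.** A one-scan subject can now be a responder, so the confirmation gap disappears. The 80% and 82% then apply to the rate as counted at the check. They would still be a little high if 10% meant the eventual rate, because some responses come later. If a share f of eventual responders is countable (f assumed), p becomes 0.10f: f = 0.9 gives 75.7% and 76.6%; f = 0.75 gives 69.0% and 66.9%. Any early look at response has this feature, whichever definition is used.

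**4. Would waiting for two scans restore the figures?** Not for the eventual rate. A response first seen at week 18 is confirmed at week 22 at the earliest (18 + 4) and week 27 on schedule (18 + 9). The check would move back by about 9 weeks while accrual continues, and some responses would still be missing.

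**5. Cohort C, both checks done and both bars followed, full opportunity to respond.** Failure means 0 in the first 15, or exactly 1 in the first 15 and 0 in the next 15.
- P(0 of 15) = 0.2059; P(1 of 15) = 15 × 0.1 × 0.9^14 = 0.3432.
- P(clear both) = 1 − 0.2059 − 0.3432 × 0.2059 = 0.7235.
- P(cross at least one bar) = 0.2765, against 0.2059 for the first check alone: an addition of 0.0707.

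At true rates of 5%, 15% and 20% the chance of clearing both is 36.7%, 89.2% and 96.0%.

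**The case for a change.** The strongest argument for a change is that a non-binding rule still informs a decision. The 80% and 82% are the only operating characteristics the team has when it sees 0 in 15, and Section 8.7 leaves open which responses count. Two statisticians could apply the same sentence to the same data and disagree. With 5 one-scan subjects and confirmed responses only, 0 in 15 has probability 0.9^10 = 35%, not 21%. One clause would settle it at no cost.

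Some of this stands. The word is undefined, and the joint Cohort C figure is absent. But disagreement would arise only when an unconfirmed response is pending at the check. In an open-label trial assessed by the investigator, that response is in front of the team, and Section 8.7 tells it to look beyond the bar. It is hard to see a cohort closed for lack of responders while one is awaiting its confirmatory scan. The 35% also depends on a count of one-scan subjects that the documents do not supply, and on the strict reading that the setting makes least likely. Section 8.7 does not require the check on the day the fifteenth subject is first scanned, so the look can be timed with maturity in mind.

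The joint figure is correct arithmetic, but it assumes that an optional second check is done and that two advisory bars are followed mechanically. ORR is a secondary endpoint reported by estimation (Section 8.6.1), so no error rate depends on it.

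**Conclusion.** No change follows. The stated probabilities are right for what they describe: one look, a 10% rate, responses as counted at that look. What is missing is a definition that analysts will fill sensibly by counting unconfirmed responses at the check and keeping confirmed response for the reported ORR. Insisting on confirmed responses would be a trade-off, not a correction: about 9 weeks' delay in a cohort that keeps enrolling, with responses first seen at week 18 still unconfirmed.

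The falls to 72%, 65% or 52% at the 15-subject check are illustrations. They rest on an assumed 3, 5 or 8 one-scan subjects, on counting confirmed responses only, and on all those subjects still being able to respond. The 72% chance of clearing both Cohort C bars needs no assumed count, but it does require both advisory bars to be followed and 10% to be the rate as counted. It concerns Cohort C alone, adds about 7 points to the risk of crossing a bar, and alters no rule, analysis or estimate.

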8.8 Multiplicity

087V73

There will be no multiplicity control in this study.

Protocol/Amendment No.: 001-08

8.9 Sample Size and Power Calculations

The overall sample size for this Phase 1 trial is expected to be approximately 235 subjects.

8.9.1 Part I Sample Size

The overall sample size for Part I is expected to be approximately 115 subjects (approximately 40 subjects each in Arm 1 and Arm 2, and 35 in Arm 3). Part A, Part C, and Part E (ATD phase) will be followed by Part B, Part D and Part F (mTPI phase) of all 3 Arms. The ATD phase will have single-subject cohorts that may enroll up to 3 subjects to account for simultaneous enrollment. The mTPI phase will have 3 to 6 subjects per cohort, based on the occurrence of DLTs; up to 14 subjects may enroll per dose level.

The sample size for Arm 1, Arm 2, and Arm 3 of this study is dependent on the number of dose levels tested and on the emerging safety data. The following scenario provides an example of the sample size.

In Arm 1 and Arm 2, in the absence of DLTs, utilizing dose increments of up to 300% for the ATD phase, and dose increments of 30% to 100% for the mTPI phase, there would be 1 subject per dose level treated at and 3 subjects per dose level treated at a dose level of The total sample size for both Arm 1 and Arm 2 would then be 30.

In Arm 3, in the absence of DLTs and with 2 possible dose cohorts for the ATD phase and dose increments of 30% to 100% for the mTPI phase, there would be 1 subject per dose level treated at and 14 subjects treated at a dose level of CCI The total sample

For dose escalation guidelines and specifications, see Section 5.2 and Table 3, Table 4, and

